In this study, we will deploy the MedRem system to obtain a small amount of clinical and social acceptance data for a particular type of stroke patient. We will have two phases of deployment. In the first phase, we will deploy the system to control/test subjects. In the second phase, we will deploy the system in homes (each for 4 weeks) in order to collect some preliminary pre-pilot data. These systems will be deployed to stroke patients. Since this is a small study we will focus on stroke victims who are able to participate with a voice command home health system (i.e. no prohibitive cognitive impairments or language deficits), who have requirements for home- based therapy regimens (i.e. physical/occupational therapy), and who require medications for secondary stroke prevention (e.g. antithrombotic therapy to prevent ischemic stroke, stroke risk factor management with blood pressure, diabetes, cholesterol medications). We will identify patients by working with [name], a neurologist in the UVA Health System, who has extensive experience collaborating on mobile telehealth projects in stroke patients.

We will focus on the clinical value of improved rehabilitation by voice-based reminder interventions. The smart watch will identify exercise and provide the frequency and type of intervention for both medications and exercise. For exercise, we will interact with the patients (via audio on the watch) at specific times of the day to determine if they have completed that exercise. These messages will be prerecorded and loaded onto the MedRem app. We will also measure heart rate and heart rhythm using the smart watch's heart monitoring capabilities and inertial measurement units using the smart watch's accelerometer, gyroscope, and magnetometer.

Then, in future proposals other issues will be investigated including ability with respect to activity of daily living skills, attitudes, depression, anxiety, long-term use, and effect of reminders related to side effects. We would also extend the work to address caregiver issues of their own health and stress and anxiety. It is also possible to extend the use of the smart watches to assess the quality of the exercise regimen.

Objectives/Hypothesis

The purpose of this study (Phase 1) is to:

Version Date: 04/09/19

Page Number: 4 of 10

- determine the feasibility of the Apple Watch medication/exercise reminder system by deploying the system to two control subjects.

The purpose of this study (Phase 2) is to:

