- assess the subjects' adherence to medications, exercise and checking heart rate (and quality of the exercise), with the use of MedRem
- assess the acceptance and usability of the MedRem system.

The hypothesis is that patients will use the system and that there are improvements in rehabilitation time and capability compared to averages for this population.

Study Design: Biomedical

1. Will controls be used? Yes.

► **IF YES, explain the kind of controls to be used.**

We will test the system with two control patients.

2. What is the study design? Case series

3. Does the study involve a placebo? No.

Human Participants

Ages: ≥18 years

Sex: All

Race: All

Subjects- see below

1. Provide target # of subjects (at all sites) needed to complete protocol.

Phase 1: 2

Phase 2: 8

2. Describe expected rate of screen failure/ dropouts/withdrawals from all sites.

Phase 1: 0%

Phase 2: 20%

3. How many subjects will be enrolled at all sites?

Phase 1: 2

Phase 2: 10

4. How many subjects will sign a consent form under this UVa protocol?

12. Phase 1 subjects will sign a Dry Run consent.

Inclusion/Exclusion Criteria

1. List the criteria for inclusion

Version Date: 04/09/19

Page Number: 5 of 10

Phase 1 (Controls)

- 18 – 75 years old
- Good general health (self-reported), with no history of CVA
- English-speaking
- Willingness and ability to comply with scheduled visits and study procedures

Phase 2 (Stroke Patients)

- 18 – 75 years old
- English-speaking
- Willingness and ability to comply with scheduled visits and study procedures
- Have requirements for home- based therapy regimens (i.e. physical/occupational therapy)
- Require medications for secondary stroke prevention (e.g. antithrombotic therapy to prevent ischemic stroke, stroke risk factor management with blood pressure, diabetes, cholesterol medications).
- Have a Modified Rankin Scale for Neurologic Disability (MDS) of 2 – 4

2. List the criteria for exclusion

Phase 1 (Controls)

- Pregnant women, fetuses, neonates, children, prisoners, cognitively impaired, non-English speaking subjects
- Prohibitive cognitive impairments or language deficits
- Does not have wireless internet connection at home

Phase 2 (Stroke Patients)

- Pregnant women, fetuses, neonates, children, prisoners, cognitively impaired, non-English speaking subjects
- Have a Modified Rankin Scale for Neurologic Disability (MDS) of 0-1 or 5
- Prohibitive cognitive impairments or language deficits

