- Significant weakness, dystonia, or spasticity that will prevent proper use and response to the Apple Watch device
- Live in nursing home or rehabilitation facility
- Does not have wireless internet connection at home

3. List any restrictions on use of other drugs or treatments. n/a

Statistical Considerations

1. Is stratification/randomization involved? No.

2. What are the statistical considerations for the protocol?

Phase 1:

The objective of Phase 1 is to determine the feasibility of the Apple Watch medication/exercise reminder system by deploying the system to two control subjects.

The primary endpoint of this phase to assess the usability of the system and to work out any technical problems. The usability will be assessed by the 'Test Patient MedRem Usability Survey.' (see attached)

Phase 2:

The objective of Phase 2 is to determine the effectiveness of the Apple Watch medication/exercise reminder system by deploying the system to stroke patients. The goal is to assess the clinical value of improved rehabilitation by voice-based reminder interventions.

The primary endpoint of this phase is to assess the patients' adherence to medications and exercise. Adherence will be measured by patient responses to questions prompted by the MedRem System.

The secondary endpoint of this phase is to assess the acceptance and usability of the system. Acceptance and usability will be measured by the Intervention Patient MedRem Usability Survey (see attached). Steps taken and distance covered data will also be collected from the Apple Watch.

3. Provide a justification for the sample size used in this protocol.

2 control subjects will suffice in determining the feasibility of the device software.

8 study subjects will suffice in determining the effectiveness of the device software. We will aim to recruit 10 subjects, accounting for a dropout rate of 20%.

4. What is your plan for primary variable analysis?

The primary variable will be analyzed by counting whether the patient responded to the MedRem system prompts and whether the patient confirms that the medication was taken or therapy exercise was completed.

5. What is your plan for secondary variable analysis?

The secondary variable will be measured based on the survey results. We will also analyze the steps taken, and distance covered data collected from the Apple Watch.

6. Have you been working with a statistician in designing this protocol? No.

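### Does the plan overstate use of the watch because it gives no analysis of patients who stop using it?

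*Combined protocol and SAP*

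**What the plan says.** Human Participants, items 1 to 3, gives 8 Phase 2 subjects to complete, an expected loss of 20%, and 10 enrolled. The form's question behind the 20% is "Describe expected rate of screen failure/ dropouts/withdrawals from all sites", so the figure pools three kinds of loss. Statistical Considerations item 3 repeats the sum under a narrower name: "We will aim to recruit 10 subjects, accounting for a dropout rate of 20" per cent.

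Objectives/Hypothesis states: "The hypothesis is that patients will use the system". The same sentence adds a claim about rehabilitation, which is not at issue here.

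On analysis, Statistical Considerations says:

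- Item 4: "The primary variable will be analyzed by counting whether the patient responded to the MedRem system prompts", together with whether the patient confirms that the medication or exercise was done.
- Item 2, secondary endpoint: "Acceptance and usability will be measured by the Intervention Patient MedRem Usability Survey". It adds: "Steps taken and distance covered data will also be collected from the Apple Watch".
- Item 5: "The secondary variable will be measured based on the survey results", again with steps and distance.

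Study Procedures, Phase 2, provides weekly follow-up contact, a telephone survey at the end of each week, and a survey call after one month. It also has the watch prompt a heart-rhythm check twice a day and keeps the time stamp of each recording. None of these contacts is stated to depend on the patient still using the watch.

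**The concern.** Where the question is whether people will use a device, giving it up is an outcome and not merely missing data. The plan treats loss as something to recruit around. It names no analysis set, no retention outcome and no rule for prompts or surveys after a patient stops. Steps and distance exist only while the watch is worn.

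If those who stop drop out of every summary, the remaining patients are the ones who liked the watch, and both use and acceptance look better than they were. With about ten patients, one or two such losses would visibly change the reported figures.

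**Working it through.** **1. The plan's own figure.** Inputs: 8 completers and 20% loss (Human Participants; Statistical Considerations item 3). 8 / (1 − 0.20) = 10, which agrees with the plan. Expected losses: 10 × 0.20 = 2.

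**2. What the losses can be.** Because the 20% includes screen failures, the number who stop after receiving a watch could be 0, 1 or 2 at the planned rate. The documents do not divide it.

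**3. Retention among watch recipients, exact (Clopper-Pearson) 95% intervals.**

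| Case | Retained | 95% interval |
|---|---|---|
| 10 given a watch, 2 stop | 8/10 = 80% | 44% to 97% |
| 9 given a watch, 1 stops | 8/9 = 89% | 52% to 99.7% |
| 8 given a watch, none stops | 8/8 = 100% | 63% to 100% |

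In the first case, a report on completers alone would also show 8/8. The intervals overlap widely.

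**4. Response to prompts over the four weeks.** The deployment length comes from Background: "we will deploy the system in homes (each for 4 weeks"). Let n be watch recipients, s those who stop, r the completers' response rate, q the stoppers' rate before stopping, and w their weeks of use. The mean of per-patient rates over the full schedule is

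[(n − s) × r + s × q × (w/4)] / n.

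The values of r, q and w are assumptions; the documents give none. With n = 10, s = 2 and q = r:

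| r (completers only) | w = 3 | w = 2 | w = 1 | Shortfall, points |
|---|---|---|---|---|
| 60% | 57% | 54% | 51% | 3, 6, 9 |
| 80% | 76% | 72% | 68% | 4, 8, 12 |
| 90% | 85.5% | 81% | 76.5% | 4.5, 9, 13.5 |

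For example, at r = 80% and w = 2: (8 × 0.80 + 2 × 0.80 × 0.5) / 10 = (6.4 + 0.8) / 10 = 72%.

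Other cases:

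- One of 9 stops, r = q = 80%: 77.8%, 75.6% or 73.3% for w = 3, 2 or 1, so 2.2, 4.4 or 6.7 points.
- No recipient stops (n = 8, s = 0): 80% under every denominator, so 0 points.
- Stoppers answer less before they leave (n = 10, s = 2, r = 80%, q = 40%): completers only 80%; all recipients while in use (6.4 + 0.8) / 10 = 72%; full schedule (6.4 + 0.4) / 10 = 68% for w = 2 and (6.4 + 0.2) / 10 = 66% for w = 1. The largest gap is 14 points.
- Outer limit, both stop at once (w = 0) at r = 90%: (8 × 0.90) / 10 = 72%, a gap of 18 points.

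Each gap needs someone to choose a completers-only count or, in some cases, a count of prompts up to stopping. The plan specifies neither.

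**5. Where a stopper would show under the plan as written.**

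- *Item 4.* Counting whether prompts were answered is a yes/no count. A patient who stays enrolled and leaves the watch in a drawer can be counted as not responding.
- *Item 5.* The surveys analysed are those in Study Procedures, taken weekly and after one month. A patient who dislikes the watch can record that in the weeks before stopping, and can be asked afterwards.
- *Other records.* Weekly contacts and the time stamps of the twice-daily rhythm checks would show roughly when use ended, although items 4 and 5 do not name them as analysis data.

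The survey forms are attachments that are not in the document, so whether they ask about stopping or its reasons is unknown.

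**The case for a change.** The best case for a change is that use is the first thing the hypothesis asserts and that the plan budgets for losing two patients in ten. It leaves the denominator to be chosen once the results are known. Item 6 says no statistician took part in the design, so sensible handling cannot be taken for granted. Item 3 claims that 8 patients suffice to determine effectiveness, which is more than a pre-pilot claim. Each stop in ten moves retention by 10 points, and writing the rule down would need no more patients or calls.

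Much of this stands as description. The analysis set, the handling of prompts after stopping and a retention outcome are all unwritten, and choosing a denominator late is a real freedom. It does not show that the plan yields a wrong result. No completers-only rule is stated, and the natural reading of item 4 works against one. The study has no test, threshold or go/no-go decision for a favourable denominator to tip. With ten patients, a per-patient listing shows the reader every loss whatever summary is chosen.

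A full set of rules would also cost more than wording. Reasons for stopping would have to be collected and judged device-related or not, patients who withdraw may be unreachable, and reminder schedules can be changed during follow-up, so the prompts due after stopping would have to be projected.

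**Conclusion.** The concern does not call for a change. The plan is silent on how patients who stop are counted, but silence is all that can be shown: item 4 can register ignored prompts and item 5 can register poor acceptance. The possible overstatement of response is 0 if nobody stops after receiving a watch, or if prompts after stopping already count as unanswered. It is 2.2 to 14 points if one or two recipients stop after one to three weeks, and at most 18 in the extreme case worked above. All the non-zero figures rest on assumed response rates and stopping times, and on a restricted count that the plan does not propose.

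For a small descriptive case series, ordinary reporting fills the gap: account for everyone given a watch, state the denominator used, give the number, timing and available reasons for stopping apart from screen failures, and keep prompts after stopping out of the medication and exercise adherence figures. The analyst can do this within the plan as it stands.

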A number of smart phone applications for medication reminder and tracking are available in app stores^{8,9}. Researchers have also designed, developed and evaluated reminder systems using smart phones^{10, 11}. However, smart phone apps are not convenient and effective enough for medication reminder and tracking. Though smart phones can be used by one hand when it is laid on or hung against some surfaces, most of the times users need to hold the phone by one hand and use it by another. Occupation of the hands for using the phones, and the attention required to use the apps justify that smartphone-based systems are significantly intrusive, and are not convenient, particularly for long-term and complex medication regimens. Also, a user is very likely to miss a reminder at home when the phone is far enough from his/her location at the time the reminder is given. For instance, a user may miss a reminder when he/she is busy in the kitchen, but the phone is in the bedroom far away from the user. Moreover, remainders may be missed while listening to songs, TVs or videos even if the phone is located near the user. In many situations like in meetings and classrooms, smart phones typically need to be kept silent, and users often forget to return the devices back to the non-silent mode when silence is not required any more. It is very likely that a user misses some reminders in such scenarios.

This study will test the feasibility of MedRem, a novel medication reminder and tracking system on wearable wrist devices, specifically with the Apple Watch 4. The study team will load the MedRem app onto two Apple Watch 4s for use during the study. As the device is

placed on the wrist, it is free from the above-mentioned limitations of smart phones. However, one of the major challenges in developing interactive systems for the wrist devices is their form factor. The touch screens available on these devices are tiny and much smaller compared to smart phones and tablet computers. MedRem enables user interactions by incorporating speech recognition and text-to-speech features along with clever interface design. The tiny display of the device is used for minimal inputs and outputs, while a user can retrieve and provide more information from/to the system through voice commands. Personalized models are built and updated over time to reduce errors in recognizing users' voice commands, and thus better user experience is provided.

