7. Will data from multiple sites be combined during analysis? No.

Study Procedures-Biomedical Research

1. What will be done in this protocol?

Phase 1:

The MedRem system will be deployed to two control subjects who will interact with the system by responding to medication and exercise reminder prompts. Subjects will be provided with oral and written information regarding the watch and MedRem system. Test subjects will not take any sham medications or exercise regimens, but will be provided a sham reminder schedule. They will simply respond verbally to prompts and press a button on the watch when finished speaking as if they are taking the medication or doing the exercise. After one week of interacting with the system, the study team will follow up with the subject and determine the functionality of the system by asking survey questions. If changes need to be made, the subject will interact with the system for one more week to test out the new changes. At the end of each week of the testing period, the subject will respond to a survey over the phone (see attached 'Test Patient MedRem Usability Survey').

Phase 2:

After a patient is identified, recruited, and consented, the study team will introduce the MedRem system to the stroke patient. The patient will be thoroughly trained before taking the device home, and will be given written information and instructions for the AppleWatch and the MedRem system. A member of the study will have to come to the patient's home to connect the apple watch to the patient's home wifi. The subject will be asked to wear the watch while awake during their daily activities. Subjects will be given contact information for a member of the study team to be available by telephone if they have questions once they begin to use the watch. The subject's physician and physical therapist, who are also members of the study team, will collect all medications and treatment regimens for the subject and give that information to the programming team. The programming team will upload the medication and treatment regimens to the MedRem system. The licensed providers, on the study team, will review the list of medication and physical therapy exercises before the information is sent to the subject's MedRem system on their Apple Watch.

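### Phase 1 plans no comparison of logged with spoken replies, so recording errors may go undetected into the Phase 2 primary endpoint, which counts those replies

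*Combined protocol and SAP*

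**What the plan says.** Statistical Considerations, item 2, gives the Phase 1 endpoint: "The primary endpoint of this phase to assess the usability of the system and to work out any technical problems". It names a usability survey for the usability part and no method for the technical part. Study Procedures, item 1, Phase 1, supplies the only method for function: after one week the team will "determine the functionality of the system by asking survey questions". The survey is given by phone at the end of each test week.

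On what the testers do, the same section says: "Test subjects will not take any sham medications or exercise regimens, but will be provided a sham reminder schedule". It continues: "They will simply respond verbally to prompts and press a button on the watch when finished speaking", acting as though they were taking the medication or exercising. A further week is possible: "If changes need to be made, the subject will interact with the system for one more week to test out the new changes". No rule says when changes are needed or when Phase 2 may begin.

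The Background section accepts that recognition is imperfect: "Personalized models are built and updated over time to reduce errors in recognizing users' voice commands". It gives no error rate and no acceptable limit.

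For Phase 2, Statistical Considerations, item 2, states: "Adherence will be measured by patient responses to questions prompted by the MedRem System". Item 4 analyses this by counting responses and confirmations.

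**The concern.** In Phase 2 MedRem is both the intervention and the measuring instrument for the primary endpoint. Phase 1 is the stage set aside for finding technical faults. A survey picks up what a tester notices and remembers, such as a missed alarm or an awkward screen. It is not a check of the stored record: a 'no' stored as 'yes', a reply filed against the wrong item, or a delivered prompt with no log entry could each go unremarked.

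The acted replies add a second gap. If testers behave as though they comply, most replies will be affirmative. The error that would inflate adherence, a negative reply recorded as a confirmation, may then never have a chance to occur. In Phase 2 such an error would be read as patient behaviour.

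**Working it through.** **The plan's own figures.** The protocol gives no figure for recording accuracy. Its one reproducible number is the Phase 2 recruitment target, 8 / (1 − 0.20) = 10, which is correct and not in dispute.

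**Inputs.** Two testers and one test week come from the protocol. Prompts per day are not stated, so I assume 2, 4 or 6. Prompts are treated as independent, although they come from only two speakers.

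**What a log check in the same week could show.** The number of checks is n = 2 testers × 7 days × prompts per day. With zero mismatches, the one-sided 95% upper limit on the error rate is 1 − 0.05^(1/n). With four reply types split evenly, each type gets n/4 checks.

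| Prompts a day (assumed) | n | Upper limit, all replies | n/4 | Upper limit, one reply type |
|---|---|---|---|---|
| 2 | 28 | 10.1% | 7 | 34.8% |
| 4 | 56 | 5.2% | 14 | 19.3% |
| 6 | 84 | 3.5% | 21 | 13.3% |

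For example, 1 − 0.05^(1/28) = 0.101 and 1 − 0.05^(1/7) = 0.348.

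The chance of seeing at least one mismatch when the true error rate is 5% is 1 − 0.95^n. Over all replies this is 76%, 94% or 99%. If the 5% rate applies to one evenly split reply type, n/4 checks give 30%, 51% or 66%.

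**Effect of weighting the script.** If half of the scripted replies are 'not taken', that type gets 14, 28 or 42 checks. The limits become 19.3%, 10.1% and 1 − 0.05^(1/42) = 6.9%.

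**What recording error could do to the Phase 2 count.** Let p be the true confirmation rate, fn the share of true confirmations not logged as such, and fp the share of true negatives logged as confirmations. The logged rate is p(1 − fn) + (1 − p)fp. All error rates here are assumed, since the documents give none.

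- p = 90%, fn = 10%, fp = 0: 0.90 × 0.90 = 81%, a fall of 9 points.
- p = 70%, fn = 10%, fp = 0: 0.70 × 0.90 = 63%, a fall of 7 points.
- p = 70%, fn = 0, fp = 10%: 0.70 + 0.30 × 0.10 = 73%, a rise of 3 points.
- p = 50%, fn = fp = 10%: 0.45 + 0.05 = 50%, no change.

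Across p = 50%, 70% and 90%, with symmetric errors of 2%, 5% or 10% or one-directional errors of 10%, the count moves by 0 to 9 points and can move either way.

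**The case against.** Several stronger statements are tempting, and the documents do not support them.

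- A reader might infer that a tester cannot see a wrongly stored reply. The protocol does not say whether the recognised reply is shown or read back. The Background describes text-to-speech and screen output, so read-back is possible. The survey is an attachment whose items are not available here, and it may ask about recognition. Even so, recall at the end of a week is not a comparison with the log.
- A reader might infer that errors will certainly pass into Phase 2. The Phase 1 endpoint includes working out technical problems, a further week is allowed, and Phase 2 has a weekly follow-up on how well the system works. None of these is a stated check of log accuracy, so the risk remains, but as a risk.
- A reader might infer that Phase 1 already has a known correct record because the schedule is sham. It does not: without a script, nobody has an independent record of what the testers said.
- A reader might infer that Phase 2 has no objective record at all. Study Procedures prompts a heart-rhythm check twice a day and keeps a timestamp for each ECG, which is an objective record for that prompt type. The primary endpoint as defined in Statistical Considerations covers medications and exercise, and no independent check of medication replies is described.
- The pooled limits flatter the check, and two speakers' prompts are not truly independent. This objection stands, which is why results are needed by reply type.
- Voice models are personalised, and Phase 1 requires good general health with no history of CVA. A clean result may not carry over to Phase 2 patients. This also stands. It limits what the check can claim but does not remove its use against gross faults.

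The study also describes itself as small and pre-pilot, which argues for a proportionate remedy.

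**Conclusion.** The point holds as a gap in the Phase 1 test. The survey is the only stated means of judging function, no comparison of logged with spoken replies is planned, and negative or absent replies may never be exercised. Recording errors may therefore go undetected into the Phase 2 count. It does not follow that errors exist or that a tester could never notice one.

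The planned week specifies no estimate of recording accuracy. A scripted week with no mismatches would bound the error rate only loosely, and more loosely for any single reply type than overall. These bounds rest on the assumed prompt frequency and on independence; the 0 to 9 point effect rests on assumed error rates. The change is a cheap improvement that should be made before Phase 1 starts.

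**What to change.** Add a Phase 1 endpoint on recording accuracy alongside the survey.

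1. Give each tester a reply script for the sham schedule covering taken, not taken, not yet and no reply, weighted towards the negative replies.
2. Compare the MedRem log with the script. Report the percentage of scheduled prompts delivered and the percentage of replies logged correctly by reply type, with exact confidence intervals.
3. State in advance how mismatches, together with the survey, decide whether the second test week already allowed is needed and whether Phase 2 can start. Say what happens if mismatches remain after that week, since the protocol provides for only one more.
4. State that the result is a screen for gross faults in two healthy speakers and may not carry over to stroke patients' speech or to their personalised voice models.

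The cost is a one-page script and one table, with no extra people, visits or devices. The downside is that a second test week becomes more likely.
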